## 7.3.2 Primary Efficacy Analysis

The primary intent to treat analysis will include all subjects who enroll and contribute at least 10 days of data to the study. The mean trajectory in decline and recovery in processing speed is unknown. Thus the primary analysis will aim to determine whether there are differences in processing speed between the BCAA dose groups and placebo, and if so, at what time periods the differences are most pronounced. The primary analysis will focus on results for the first 10 days of the study when we anticipate that the majority of subjects will be highly compliant. We will model processing speed as a function of dose and day of study and will allow differences between dose groups to vary as a function of time through a series of interaction terms. To ensure that the number of interaction terms does not become too large, we will consider groups of two to four time points, looking specifically at whether

04/06/2018 V 0.16

there are differences between any of the dose groups and placebo at Days 1-2, 3-6, 7-10, 11-14, 15-18, 19-21. The primary analysis will consider three key time periods, Days 3-6, 7-10 and 11-14 when we expect differences in processing speed between the BCAA-treated groups and placebo to be largest. Since processing speed differs with age, the model will be adjusted for age to account for any imbalances in age between dose groups. A mixed effects model will be used to account for correlations between repeated measurements on individual subjects. Likelihood ratio tests will be employed to specifically test whether there are differences in mean processing speed between placebo and any of the BCAA doses at the three key time periods. These three global tests will be conducted at a family-wise error rate of 0.05, using a Bonferroni correction to account for the three individual global tests. If statistical significance is achieved for the global test, we will then compare individual dose levels to placebo within time periods, again using a correction for four multiple tests per key time period.

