We note that with five treatment groups and 21 time points, there are a very large number of possible hypothesis tests that can be carried out with these data. If all of these tests were carried out without adjusting for multiple comparisons, we would undoubtedly find spurious associations. On the other hand, adjusting for large numbers of multiple comparisons substantially reduces the statistical power of a study. By focusing our testing for the primary efficacy analysis on three key periods where we adjust for a limited number of tests, we balance the need for a rigorous statistical testing procedure with a need to maintain statistical power.

An analysis of the Day 1-2, 15-18 and 19-21 data will follow the same format, but will be considered secondary and will not be formally corrected for multiple testing. In addition to hypothesis testing, we will estimate and plot means and confidence intervals for each group at each time point. This analysis will guide the recommendation for dose levels and evaluation times for the primary analysis in future efficacy studies.

With concerted efforts from our study coordinators and study staff we are hopeful that we can maintain excellent compliance throughout the study. In particular we expect good compliance early in the study when patients are highly motivated to feel better and return to school, work and play. However, we allow that some patients may have difficulty with compliance due to their injury, or become non-compliant once their symptoms improve. As part of this feasibility study, we will explore patterns of missing data, in particular how they may relate to the observed response (e.g. more missing data in those subjects who show better or worse processing speed) to compliance (e.g. more missing data in subjects who regularly fail to consume their supplements) and to demographics e.g. gender, age. This information will be valuable in planning future efficacy trials, and will guide our efforts to adjust for missing data. For example if the probability of missing data is associated with outcome, then non-ignorable missing data methods will be needed, whereas missing at random assumptions will be valid if the missing data can be explained by covariate information.

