## 7.4 Sample Size and Power

The primary analysis of the processing speed data is broadly based, reflecting the fact that that this is a feasibility study in which we have limited knowledge regarding the temporal patterns of decline and recovery in human neurocognitive functioning following concussion. We hypothesize that BCAA-treated groups will differ from placebo at specific time periods. The power calculation is based on comparisons of each dose group to placebo at each of the key time periods. These time periods each encompass three daily measurements per subject. With 10 subjects per dose group, and three repeated measurements per subject we have 80% power to detect mean differences in processing speeds between the BCAA group and the placebo group on the order of 0.122 seconds. Putting this in the context of a mean processing speed for healthy individuals of ages 14 to 34 of 2.46 to 2.51 seconds (Axon Sports unpublished), means that detectable differences between groups are on the order of 5% of the mean of a healthy individual. The analysis is based on a standard deviation in healthy individuals of 0.08, which we inflated to 0.10 based on our experience with injured or sick subjects, where variances are generally larger than their healthy counterparts. The intra-class correlation coefficient was set to 0.5. The calculation assumes a two-sided family-wise Type I error rate of 0.05 and uses a Bonferroni correction with four contrasts for each time period. The overall sample size is thus 50 subjects. We will consider a subject who contributes data up until and including at least Day 10 to be "evaluable for efficacy." We conservatively anticipate that no more than 72 subjects will be enrolled in order to achieve 50 evaluable subjects. We anticipate that it will take us approximately 12-18 months to recruit these subjects.

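### The missing-data rule in Section 7.3.2 cannot separate ignorable from non-ignorable dropout, no sensitivity analysis covers unseen scores, and the ten-day primary set weakens the mixed model's validity

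*Combined protocol and SAP*

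**What the plan says.** All the relevant text is in Section 7.3.2 of the combined protocol and SAP.

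- **Model.** "A mixed effects model will be used to account for correlations between repeated measurements on individual subjects". Likelihood ratio tests compare BCAA doses with placebo at Days 3-6, 7-10 and 11-14. The stated terms are dose, time, their interactions, and age.
- **Primary set.** "The primary intent to treat analysis will include all subjects who enroll and contribute at least 10 days of data to the study".
- **Expected reasons for missing data.** "some patients may have difficulty with compliance due to their injury, or become non-compliant once their symptoms improve". Section 7.3.3 expects test completion to start falling at around Days 10 to 14 as subjects recover, which overlaps the third key period.
- **Exploration.** Patterns of missing data will be examined for "how they may relate to the observed response (e.g. more missing data in those subjects who show better or worse processing speed"), and also against compliance and demographics. This information "will guide our efforts to adjust for missing data".
- **Rule, given as an example: when to leave MAR.** "if the probability of missing data is associated with outcome, then non-ignorable missing data methods will be needed".
- **Rule, given as an example: when to keep MAR.** The contrasting half of the same sentence holds that "missing at random assumptions will be valid if the missing data can be explained by covariate information".

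No non-ignorable method is named, and no sensitivity analysis for dependence on unseen scores is specified.

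**The concern.** The rule draws its line in the wrong place. Missingness that depends on scores already recorded is MAR. A likelihood mixed model is valid under it, provided the model is correctly specified and uses all the observed data. Missingness is non-ignorable when, given everything observed, it still depends on the scores that were not seen. No check on recorded data can establish or exclude that.

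The covariate half of the rule is true as a sufficient condition but too narrow as a definition, because it leaves observed scores out of MAR. It also helps only if the explaining covariates are in the model, and the stated primary model adjusts for age alone.

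The plan itself expects subjects to stop testing for reasons linked to recovery or injury, so the rule is likely to come into use. A method would then be chosen after the data are seen, from an association that cannot show which method is needed. If the association looked absent or explained by covariates, nothing in the plan would probe unseen-score dropout. Because the missing-data findings are meant to inform later efficacy trials, the misclassification could carry forward.

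**Working it through.** **1. The plan's own figure.** Inputs from Section 7.4: SD 0.10, intra-class correlation 0.5, 10 subjects per group, three measurements, and two-sided 0.05 divided by four contrasts = 0.0125.

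- SD of a three-day mean = 0.10 × √((1 + 2 × 0.5)/3) = 0.0816.
- Standard error of one dose-placebo contrast = 0.0816 × √(2/10) = 0.0365.
- Detectable difference = (z for two-sided 0.0125 + z for 80% power) × 0.0365 = (2.498 + 0.842) × 0.0365 = 0.1219 s.

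This reproduces the stated 0.122 s, so the same SD and correlation are used below. The planned loss is 1 - 50/72 = 30.6% of enrolled subjects not evaluable.

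**2. Simulated dropout.** The assumptions that are not in the documents are:

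- a true difference of -0.050 s on Days 3-14 (negative means faster on BCAA)
- a placebo mean falling by 0.10 s from 2.60 s by Day 14
- permanent dropout from Day 3, with daily log-odds -3.4 ± 12 × (score - 2.52)

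The driving score is either the last observed one (MAR) or the current unseen one (not at random). In the same-direction case, faster subjects leave more often in both arms. In the opposite-direction case, faster placebo subjects and slower BCAA subjects leave. Between 60% and 77% per arm remain at Day 10. Each scenario has six runs of 1,000 subjects per arm, two arms, fitted with a maximum-likelihood random-intercept model. Because dropout is permanent, having ten days of data and reaching Day 10 coincide.

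Estimates for Days 11-14 (truth -0.050; Monte Carlo SE about 0.001 to 0.002):

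| Dropout depends on | Direction | Mixed model, all data | Mixed model, ten-day set | Raw observed means |
|---|---|---|---|---|
| Observed score | Same | -0.051 | -0.043 | -0.041 |
| Observed score | Opposite | -0.052 | -0.085 | -0.093 |
| Unseen score | Same | -0.048 | -0.040 | -0.038 |
| Unseen score | Opposite | -0.065 | -0.090 | -0.097 |

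- Observed-score dropout, all data: essentially unbiased.
- Observed-score dropout, ten-day set: (0.050 - 0.043)/0.050 = 14% too small, or (0.085 - 0.050)/0.050 = 70% too large. The larger error, 0.035 s, is about one standard error of a planned contrast (0.0365).
- Unseen-score dropout, all data: (0.050 - 0.048)/0.050 = 4% too small, or (0.065 - 0.050)/0.050 = 30% too large.

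A second simulation with the same true value, again under assumed dropout, gave -0.054 and -0.052 with all data and -0.044 and -0.092 in the ten-day set.

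**3. Can the check tell the mechanisms apart?** In 400 simulated trials per mechanism, each with 70 subjects (five arms of 14) and same-direction dropout, missingness was tested against the last observed score at 0.05:

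| True mechanism | Trials with a significant association |
|---|---|
| Unrelated to scores | 6.5% |
| Observed score (MAR) | 100% |
| Unseen score (not at random) | 90% |

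Repeated scores on one subject are correlated, so unseen-score dropout also leaves a trace in the recorded scores. A positive check therefore does not say which mechanism is at work.

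**The case against.** The strongest reply is that the sentence speaks of outcome without qualification. If it means the score that would have been seen, the first clause is correct, and the covariate clause is true as far as it goes. But the sentence illustrates how the exploration will be used, and that exploration concerns the observed response, compliance and demographics. Association with unseen scores cannot be tested, so on the charitable reading the rule could not be applied.

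Two stronger readings are tempting, and neither is supported.

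- **That the plan would discard its mixed model once the association appears.** The model is stated unconditionally, the rule is offered as an example that guides adjustment, and a non-ignorable analysis could sit beside the primary one.
- **That the rule would miss the dropout that causes bias.** In the simulation it flagged unseen-score dropout in 90% of trials. Its fault is poor discrimination.

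It is also fair to say that this is an exploratory feasibility trial and that the simulated dropout is assumed. The size and sign of bias depend on that assumption: under same-direction unseen-score dropout, the all-data estimate was only slightly off (-0.048). The plan does not say that raw means will be plotted, so the last column of the estimates table shows a risk and not a stated procedure.

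**Conclusion.** The concern holds in this form. The example rule classifies missingness related to processing speed as non-ignorable and ties MAR to covariates, although the only association that can be checked is compatible with MAR. The check cannot separate the two mechanisms (100% against 90% positive), and the plan prespecifies nothing for dependence on unseen scores.

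The MAR defence is also not fully available to the plan as written, because the ten-day set drops data the mixed model relies on. Across the simulations with a true difference of -0.050, all-data estimates under observed-score dropout were about -0.051 to -0.054, and ten-day-set estimates about -0.043 to -0.092.

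That all-data likelihood analysis is valid under MAR follows from theory, given a correctly specified model. The sizes rest on the assumed trajectory and dropout model and are illustrative, not predictions for this trial.

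**What to change.** Replace the example rule in Section 7.3.2 with:

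> Missingness that depends on observed scores, arm and covariates is treated as MAR. The primary analysis is the likelihood mixed model on all observed days from all randomised subjects with any processing-speed data. Whatever pattern is seen, a prespecified sensitivity analysis for non-ignorable dropout (for example delta-adjusted or pattern-mixture, over a stated range of shifts) will be reported.

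Amend the primary-set sentence to match, and keep the ten-day set as a supportive analysis. State that the plotted means are model-based. The exploration of missing-data patterns can stay as a descriptive aim, but it should not decide whether the sensitivity analysis is run. The shift range is for the study team to choose and write down before unblinding.

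The cost is a paragraph of wording and one extra analysis. Subjects with few days of data would enter the primary model.

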# ABBREVIATIONS AND DEFINITIONS OF TERMS

FROTOCOL STRUFSIS			
Study Title	HIT HEADS Trial: Head Injury Treatment with Healthy and Advanced Dietary Supplements: A randomized, placebo-controlled, double-blinded, therapeutic exploratory clinical trial of branched chain amino acids (BCAA's) in the treatment of concussion		
Funder	Dana Foundation		
Clinical Phase	Phase II		
Study Rationale	Annually, between 100,000 to 140,000 children present to the emergency department for concussion in the United States.  The Centers for Disease Control now estimates that 1.6 - 3.8 million sports related concussions occur each year in the United States. A large proportion of these patients have enduring cognitive and neurobehavioral problems. Concussion is a heterogeneous insult to the brain that precipitates a complex pathophysiological process that can result in a cascade of deleterious side effects. At present, there are no proven therapies to mitigate or prevent the neurocognitive and neurobehavioral consequences of concussions. The limbic hippocampus, a brain structure crucial for learning and memory, is often damaged in concussion. In preclinical studies in our laboratory, analysis of ipsilateral hippocampi isolated from mice after traumatic brain injury (TBI) demonstrated that only the concentrations of the three BCAA's (valine, isoleucine, and leucine) were significantly altered (reduced) after injury. When these brain- injured animals received dietary supplementation with BCAA's, the concentrations of these amino acids were restored in the injured hippocampus and the injured animals demonstrated significant cognitive improvement to levels comparable to those obtained in non-injured control animals. In light of these results and the increasing awareness and morbidity associated with concussion, we are proposing a pilot therapeutic exploratory clinical trial to determine the effects of BCAA's in reducing the neurocognitive side effects of concussion injury.		
Study Objective(s)	Primary		
	
 
To determine whether, compared to placebo treatment, administration of BCAA's, at one or more doses, after a concussion improves processing speed recovery at one or more time-periods post concussion.
 
		
	
 
Secondary
 
Determine whether administration of BCAA's improves neurocognitive recovery compared to placebo for the cognitive domains of attention, learning, and working memory.
 
		

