### 2.5 Relevant Literature and Data

#### 2.5.1 Computerized Cognitive Testing

Neuropsychological testing provides a valuable mechanism to detect both obvious and subtle impairments in cognitive functioning after concussion. Several computerized testing batteries are commercially available to evaluate patients after concussion. The Axon Sports Computerized Cognitive Assessment Tool (CCAT) is optimal for use in a context where frequent repeated measurements of cognitive performance are required. The CCAT consists of four computerized cognitive tests, derived from theoretical and developmentally sensitive principles, allowing this tool to be sensitive to any cause of cognitive performance change in individuals over time. The tasks themselves measure processing speed (via a simple reaction time task), attention (via a choice reaction time task), learning (via a one card learning task),

and working memory (via a one-back task). These tests have been widely validated in both healthy and concussed individuals. Normative scores exist for men and women greater than 18 years, as well as, children and adolescents aged 10-18. Studies have shown that task performance is similar between 16-18 year olds and adults.

Prior research has demonstrated the sensitivity of the CCAT tests to neurological impairment, including mild TBI and concussion. The reliability and metric properties of the tests have been described and normative data are published. Numerous publications have demonstrated that the Axon Sports CCAT has minimal practice effects (making it ideal for repeat testing as in this proposal), and good criterion, construct, test-retest, and ecological validity. The CCAT tasks have been shown to be sensitive to concussion-related cognitive decline and symptomatic athletes have greater impairments as measured by the CCAT than asymptomatic athletes.

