# 3.1 Primary Objective

The primary objective of this study is to determine whether, compared to placebo treatment, administration of BCAA's, at one or more doses, after a concussion improves processing speed recovery at one or more time-periods post concussion. In the event that differences are observed, we will determine whether differences in processing speed between BCAA-treated and placebo-treated groups reflect differences in the maximum level of impairment and/or increases in the subsequent speed of improvement.

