## 4.4 Study Population

## 4.4.1 Inclusion Criteria

- 1) Males and females, ages 11 34 years, of any race.
- 2) Weight at least 40kg.
- 3) Subjects who had a concussion, as diagnosed by a qualified physician or advanced practice provider, within the 72 hours prior to enrollment.
- 4) Ability to have daily email and internet access.

- 5) Post-menarchal females must have a negative urine pregnancy test and must use an acceptable method of contraception including abstinence, a barrier method (diaphragm or condom), Depo-Provera, or an oral contraceptive for the duration of the study.
- 6) Subjects must, in the opinion of the referring physician, have the capacity to provide informed consent, defined by: 1) the ability to communicate; 2) the ability to assess their understanding of the treatment; 3) the ability to understand the risks and benefits of the treatment; and 4) the ability to understand the risks and benefits of not embarking on the treatment.
- 7) Informed consent by the subject, or for subjects <18 years old both informed consent by a parent/guardian and child assent.

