In addition to the primary analysis, this feasibility study will consider several approaches to modeling a smooth function for the trajectories of the individual processing speeds. The first model will fit non-linear curves to the trajectory of processing speed for the dose groups  $04/06/2018 \vee 0.16$ 

and then compare the mean curve for the BCAA dose groups to the placebo group, using an interaction term that allows differences between groups to vary over time. The basis for this model will be a smoothing spline. This first model assumes that the trajectories are smooth over time, albeit somewhat different between groups. We will carry out a hypothesis test of the difference between the groups using a likelihood ratio test for models with and without terms for the treatment effect and treatment by time interactions. A second model conceptualizes an initial increase in processing speed followed by a period of gradual improvement and by a transition where processing speed plateaus. This transition is of interest as we hypothesize that it represents the time when processing speed has returned to baseline. Here we anticipate a model using a quadratic with a change-point, with separate baseline functions for the dose and placebo groups and separate change-points. Correlation between repeated measurements on the same individual over time will be modeled using random effects i.e., a mixed effects model will also be used for these analyses.

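### The exploratory change-point model reads the start of the plateau as return to baseline, but a change-point shows only when improvement stops, not the level reached

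*Combined protocol and SAP*

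**What the plan says.** Section 7.3.2 introduces this work as additional: "In addition to the primary analysis, this feasibility study will consider several approaches to modeling a smooth function". The second model has processing speed first rising (getting slower), "followed by a period of gradual improvement and by a transition where processing speed plateaus". It is to be a quadratic with a change-point, "with separate baseline functions for the dose and placebo groups and separate change-points". The transition is interpreted as follows: "This transition is of interest as we hypothesize that it represents the time when processing speed has returned to baseline".

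Section 7.3.2 does not define baseline for this purpose. It does not say that plateau levels will be estimated, compared between arms or set against any norm.

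Three other places bear on the reading:

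- Section 4.4.1 enrols after the injury: "Subjects who had a concussion, as diagnosed by a qualified physician or advanced practice provider, within the 72 hours prior to enrollment". Table 1 schedules the cognitive test (CCAT) daily in the treatment phase only.
- Section 3.1 will ask, if arms differ, whether the differences "reflect differences in the maximum level of impairment and/or increases in the subsequent speed of improvement". The final level reached is not listed.
- Section 2.5.1 notes that reference values exist: "Normative scores exist for men and women greater than 18 years, as well as, children and adolescents aged 10-18". Section 7.3.2 does not use them.

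**The concern.** A change-point estimates the day the curve becomes flat. It equals the day of return to baseline only if the flat part lies at baseline, and the trial cannot check that from its own data. Every CCAT score is taken after injury, and all five arms are concussed subjects. If baseline meant the enrolment score, that score is already post-injury, and Section 7.1 expects function to worsen after it.

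Because change-points and curves are fitted separately by arm, plateaus may differ between arms. An arm that levels off early at an impaired level then has the earlier change-point. Under the stated interpretation it would be reported as back to baseline sooner, although it ended worse. At stake is what this model says about recovery time, in a study meant to inform the design of later trials.

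**Working it through.** **Inputs.** From Section 7.4: SD 0.10, intra-class correlation 0.5, 10 subjects per arm, three measurements per period, two-sided 0.05 divided by four contrasts (0.0125), detectable difference 0.122 seconds, healthy mean 2.46 to 2.51 seconds. Higher values are slower. All trajectories below are assumptions.

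**The plan's own figure.** SD of a three-day mean = 0.10 × √((1 + 2 × 0.5)/3) = 0.0816. Standard error of a difference = 0.0816 × √(2/10) = 0.0365. Detectable difference = (2.498 + 0.842) × 0.0365 = 0.122. The stated figure reproduces under the normal approximation.

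**Direction.** With starting impairment S, improvement r per day and change-point τ, the plateau is S − r × τ. If S and r are equal in two arms, the plateaus differ by r times the gap in change-points, and the earlier change-point always goes with the worse plateau. If plateaus are equal, an earlier change-point does mean earlier recovery. The stated reading therefore needs the plateau to be known.

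**Worked example.** Both arms start 2.0 SD impaired and improve 0.2 SD per day.

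- Early-stopping arm, plateau 1.0 SD impaired: (2.0 − 1.0)/0.2 = Day 5.
- Later-stopping arm, plateau 0: (2.0 − 0)/0.2 = Day 10.
- Difference at plateau: 1.0 SD = 0.10.

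**Does noise hide the pattern?** A simulation used a quadratic joined to a flat plateau over Days 0 to 21, with 10 subjects per arm, SD 0.10, correlation 0.5, a common start of 2.75 seconds and 2,000 runs per scenario. The change-point was fitted by least squares to daily arm means, with no missing data. Starting levels are equal; rates of improvement are not exactly equal.

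| Early-stopping arm | Later-stopping arm | Median fitted change-points | Early-stopping arm fitted first |
|---|---|---|---|
| Day 7 at 2.60 s | Day 14 at 2.50 s | 7 v 14 | 99.9% |
| Day 8 at 2.575 s | Day 12 at 2.50 s | 8 v 12 | 97.9% |
| Day 8 at 2.55 s | Day 12 at 2.50 s | 8 v 12 | 98.9% |

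The worse arm reads 4 to 7 days faster while it is 0.05 to 0.10 seconds slower throughout Days 15 to 21. Against the upper healthy value of 2.51 seconds the order reverses: the later-stopping arm's mean reaches it by Day 9.6 to 11.2, and the early-stopping arm's does not by Day 21.

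**Would the other analyses show a 0.10 gap?** For one dose-placebo contrast at 0.0125 on a three-day mean: 0.10/0.0365 = 2.74, and 2.74 − 2.50 = 0.24, so power is about 60%. In the late windows, tested at an uncorrected 0.05:

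- Days 19-21: 2.74 − 1.96 = 0.78, power about 78%.
- Days 15-18, four days: SD = 0.10 × √(2.5/4) = 0.0791, standard error 0.0354; 2.83 − 1.96 = 0.87, power about 81%.

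These analyses would often show the gap, but not always. Nothing requires them to be read beside the change-point.

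**The case against.** The strongest reply is that nothing formal depends on this model. It is additional to the primary analysis, the interpretation is worded as a hypothesis, and no endpoint, test or decision uses the change-point. Section 7.3.2 also plots means and confidence intervals for each group at each time point, tests Days 15-18 and 19-21, and fits a spline to the whole curves. That stands, and it limits the point to how an exploratory result is described. It does not remove it: the interpretation is written down, and no step checks it.

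A reader might infer several stronger claims that the documents do not support:

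- **That dose selection is misdirected.** Section 7.3.2 bases the dose recommendation on the window comparisons and plotted means, which it sets out before introducing the change-point model.
- **That the primary conclusion is reversed.** The primary tests do not use the change-point. Section 3.1 asks about speed of improvement, which is equal in both arms of the worked example.
- **That the protocol expects impaired processing speed at Day 21.** The synopsis does say "A large proportion of these patients have enduring cognitive and neurobehavioral problems", but this is general background. Section 7.3.3 expects subjects to begin feeling better around Days 10 to 14. The background makes an impaired plateau plausible; it does not predict one, still less one that differs by arm.
- **That daily testing creates the plateau through learning.** Section 2.5.1 reports minimal practice effects, Section 6.2.1 adds a practice session, and learning would occur in every arm.

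Section 10.6 mentions a clinical battery before enrolment, but does not describe it as a pre-injury score, and Section 7 makes no use of it.

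**Conclusion.** The point holds as an interpretive fault in an exploratory analysis. The change-point cannot be called return to baseline from the data this trial collects. Where arms share a starting level and rate of improvement, the stated reading favours the arm that ends worse: by 5 days in the worked example and by 4 to 7 days in the simulations, against a final deficit of 0.05 to 0.10 seconds.

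Those sizes rest on assumed trajectories in which one arm both stops earlier and plateaus worse; no document says this will happen. The direction rests only on what a change-point measures. If all arms plateau at the same level, the ordering of change-points is sound. The primary window tests and the dose-recommendation analyses stand as planned.

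**What to change.** In Section 7.3.2:

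1. Describe the change-point as the time improvement stops, and remove the statement that it represents return to baseline.
2. Beside each arm's change-point, report its estimated plateau level and the difference in plateau from placebo with a confidence interval.
3. Describe an earlier change-point as faster recovery only when it is read jointly with a plateau that is not worse than placebo's. Otherwise report the change-point difference as inconclusive, or as an earlier stop at a worse level.
4. Optionally, show the plateaus against age-specific CCAT norms as descriptive context. The healthy mean in Section 7.4 covers ages 14 to 34, while enrolment starts at 11.

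A recovery definition based on entry into a normal range is not advised. If the range were the healthy mean ± 1.96 × 0.08 = ± 0.157 (an assumed width), both arms of the worked example, starting 0.20 above the mean and improving 0.02 per day, would enter it at (0.20 − 0.157)/0.02, about Day 2. The difference between them would disappear.

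The change needs no new data. Its cost is imprecision. With seven plateau days per subject, 10 subjects per arm and nothing missing, the SD of a subject's mean is 0.10 × √((1 + 6 × 0.5)/7) = 0.0756. The standard error of a difference is 0.0756 × √(2/10) = 0.0338, and the 95% interval about ± 0.066, before allowing for estimation of the change-point. Some change-point differences will therefore have to be reported as inconclusive.
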